## 1.0 Objectives / Specific Aims

Improving treatment for anxiety and related conditions is essential, as anxiety disorders, for example, have a lifetime prevalence of 16.6% (Remes et al., 2016) and remission rates at only 51% after frontline exposure therapy (Springer et al., 2018). Enhancing acceptability and improving treatment refractory rates are *key*. Transcutaneous auricular vagus nerve stimulation (taVNS) is a brain stimulation candidate for disorders characterized by sympathetic hyper-activity (i.e., fight-or-flight; Badran et al., 2018c), including but not limited to generalized anxiety disorder, social anxiety disorder, panic disorder, and posttraumatic stress disorder. In fact, taVNS is thought to target transdiagnostic mechanisms, those mechanisms which are not diagnosis specific and cut across psychiatric illnesses. These include inflexible stress responses, heightened anxious arousal, and impaired cognitive processing (Deuchars et al., 2018). There are many advantages to taVNS over other stimulation technology, as it is non-invasive, affordable, and safe enough to implement at home or in the cognitive-behavioral therapy (CBT) clinical setting, without immediate MD oversight. A major limitation to the development of therapeutic taVNS is a lack of evidence for the optimal stimulation intensity. Failing to fully assess dose responses and mechanisms of taVNS is a major barrier to implementation in transdiagnostic interventions.

To establish the clinical viability of taVNS, it will be essential to determine optimal dosing to impact cognitive control and fear learning and associated biomarkers. Recent research suggests that there is a bidirectional relationship between sympathetic responses and cognitive control implicated in adaptive learning processes (Taylor et al., 2019; 2020). Also, anxiety is linked to heightened perception of heart rate changes (subjectively and neurally; Judah... Taylor & Grant, 2018), both factors which in turn influence cognitive functioning and learning processes, fear or otherwise, and this cascade may be modulated via vagal tone. Therefore, this study will determine the optimal taVNS dose and its influence on the course of fear learning and basic cognitive processes during goal-directed activity, while evaluating the psychophysiological profile in each context.

In order to develop therapeutic taVNS for psychiatric problems, a necessary first step is to establish the appropriate parameters that will modulate cognitive and affective responses among healthy participants. We will first recruit 45 healthy participants (randomized to 9 different dose durations) to determine the dose-response curve for taVNS on a range of vagally-mediated physiological measures and subjective mood. At a single session, heart rate variability (HRV), skin conductance (SC), and electroencephalography (EEG) will be measured at baseline, concurrently with stimulation, during learning and cognitive tasks and finally during a recovery period. Utilizing rest, learning and recovery conditions concurrent with multiple physiological measures we will demonstrate whether there is process- or physiological modality-specific modulation or co-activation across domains and measures. Our team of experts in brain stimulation, neuroscience, and psychophysiology are uniquely suited to accomplish these tasks. After establishing the dose-response curve, the findings of our dosing may be evaluated an additional sample of 45 participants seeking treatment for anxiety or trauma related disorder.

An additional goal of this study is to evaluate invasive vagus nerve stimulation (VNS) to determine how taVNS relates to other established forms of brain stimulation via the vagus nerve. VNS is currently FDA approved for depression and epilepsy, and research has indicated that patients also report decreased anxiety symptoms. Therefore, patients with previously implanted VNS, will be invited to complete this study. They will be administered similar tasks as participants who receive taVNS, and a full psychophysiological profile will be assessed. This study will only recruit individuals who currently have implanted VNS, given the invasive procedure. Although VNS is FDA approved, nearly 150,000 patients have received VNS worldwide over the past 25 years. Therefore, limited patients in the study area have received VNS, so this study expects to recruit <5 patients for this study goal.

**Aim 1. Establish the dose-response curve secondary to transauricular vagus nerve stimulation (taVNS) for vagally-mediated physiological indicators at rest.** We hypothesize that a dose-response curve will be observed with higher doses than typically administered in taVNS protocols being more efficacious in affecting physiological responding. Exploratory Aim 1a. Examine whether dose-response curves vary as a function of physiological measure (e.g., EEG/HRV, etc.). Exploratory Aim 1b. Examine whether a dose-response curve emerges for state measures of mood and interoceptive sensitivity.

**Aim 2. Establish the dose-response curve secondary to transauricular vagus nerve stimulation (taVNS) for vagally-mediated physiological indicators during fear and cognitive challenge.** We hypothesize that higher doses than typically administered in taVNS protocols will be more efficacious in affecting physiological responding and performance. Exploratory Aim 2a. Examine whether dose-response curves vary as a function of different physiological measures. Exploratory Aim 2b. Examine whether a dose-response curve emerges for cognitive and/or fear learning performance.

**Aim 3. Assess tolerability and feasibility among a sample of participants with anxiety and trauma related symptoms.** We hypothesize that utilizing taVNS among participants with anxiety and trauma symptoms will be well tolerated and will modulate autonomic arousal and fear processes, as indicated in physiological indicators.

**Exploratory Aim 3.** Examine whether invasive VNS and taVNS result in similar modulation of physiological measure (e.g., EEG/HRV, etc.), state measures of mood and interoceptive sensitivity, and across similar cognitive and affective tasks.

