Participants will be randomized to one of 9 dose durations with 5 participants per dose, increasing in 10 minute increments of active stimulation, ranging between 10 and 90 minutes of stimulation. All active sessions per dose will be delivered contiguously and at the end of the stimulation period, and sham stimulation at the beginning. This is to ensure that all participants have the same lapse of time between pre- and post-stimulation recording. That is, if a participant is randomized to 60 minutes of active stimulation, the first 30 minutes would be sham stimulation. After establishing the optimal dose-duration a sample of treatment seeking individuals will be recruited. This dose will be administered to individuals with anxiety and trauma symptoms to ensure that effects are sustained and to determine feasibility and tolerability.

An additional group of individuals with implanted VNS also will be evaluated after 30 minutes of stimulation. Patients at MUSC who participated in the Microtransponder Vivistim trial or other research/treatments involving VNS will be recruited to complete similar cognitive and affective tasks while psychophysiological responses are measured across 3 sessions: control (no stimulation), implanted VNS, and noninvasive taVNS. This will serve as a comparator for whether taVNS is activating similar brain and physiological regions as invasive forms of vagus nerve stimulation. This will also indicate whether mechanisms of taVNS and VNS are comparable. In order to truly determine comparability of these two forms of VNS, it is imperative to assess within subject brain, body, cognitive, and emotional responding across both implanted and non-invasive VNS.

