## **6.0 Number of Subjects**

This study will recruit 90 community individuals who meet the above inclusion and exclusion criteria, 50% of which will be female. Participants ( $n = 45$ ) who are healthy controls will be recruited to establish the dose response curve. Then this dose will be administered to 40 individuals with anxiety and trauma related symptoms. Participants with implanted VNS ( $n = 5$ ) will be recruited for similar procedures.

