After all electrodes are attached, a 1) baseline (5-10 min) physiology measurement will be taken. Then stimulation will begin. See additional information in Section 3.0 (Intervention to be Studied). Participants in the taVNS group (not having implanted VNS) will be randomized to one of 9 doses with 5 participants per dose, increasing in 10 minute increments of active stimulation. All active sessions per dose will be delivered contiguously and at the end of the stimulation period, and sham stimulation at the beginning. This is to ensure that all participants have the same lapse of time between pre- and post-stimulation recording. That is, if a participant is randomized to 60 minutes of active stimulation, the first 30 minutes would be sham stimulation.

For participants with previously implanted vagus nerve stimulation devices, stimulation will be delivered for 30 minutes. They will subsequently be invited to revisit the lab to receive non-invasive taVNS delivered in a comparable manner to the healthy subjects for 30 minutes.

Additional physiology measurements will be taken 2) concurrent with stimulation and during a final recovery measurement (5-10 mins) after stimulation has concluded.

During the base, recovery, and during 3 time points during the 90-minute stimulation period (i.e., 30 minutes, 60 minutes, and 90 minutes), a Passive Auditory Oddball Task will be administered. During this task a relaxing movie (i.e., silent sand art film) is presented concurrent with standard and deviant tones; MMN task from the ERP Compendium of Open Resources and Experiments - ERP CORE; Kappenman et al., 2020; Eriksen & Eriksen 1974).

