## 12.0 Data Management

Power: Dose-response studies are not powered in the traditional manner. To resolve the shape of the continuous dose response function, it is statistically more efficient to select more doses as opposed to more participants (O’Quigley & Conaway, 2010; Kuljus et al., 2006). The number of observations within each dose primarily accounts for sampling variability, which could be achieved with 2-3 observations. Capturing variability is essential to the planned analyses, which underweight the points of greatest variability in estimating the response curve. Thus, the sample size of  $N = 45$  was determined sufficient to accomplish Aim 1 to establish a dose-response curve. Of note, [name] is running three funded projects with these dose-response techniques in optimizing repetitive transcranial magnetic stimulation (rTMS). An additional, sample of 45 participants are included in the case of data loss and to replicate dose-response findings/assess feasibility/tolerability on participants with anxiety or trauma related disorder or symptoms.

Analyses: The psychophysiological data will be processed using standard protocols which have previously been used in this lab and in various other studies (Sege et al., 2017, 2018, Taylor et al., 2020; Grant et al., 2015), and according to published guidelines (Blumenthal et al., 2005; Boucsein et al., 2012; Gatchel et al., 1973; Keil et al., 2014).

Dose-response relationships will be assessed using the multiple comparisons procedure with modeling (MCP-Mod) approach pre- to post-stimulation changes in physiology and behavior. To determine the reliability of a dose response, MCP-Mod fits a set of pre-specified candidate dose-response curves to the data using a multiple-comparisons technique. The pre-specified dose-response curves to be tested would be Emax, logistic, and linear. Significant curves would then be used to develop inferences on optimal doses for a follow-up adaptive-dosing design, with doses more finely resolved around the probable point of maximal efficacy as determined in this project.

**Confidentiality and Quality Control:** All study personnel will complete Social-Behavioral-Educational research CITI training, and also complete in-lab training regarding data security practices. Study personnel will be trained in the IRB protocol. The investigator, and co-investigators will be available to monitor data collection to ensure quality, confidentiality, and adherence to the IRB protocol.

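### Aim 3 hypothesises that taVNS will modulate arousal and fear in the anxiety/trauma cohort, but on the likeliest reading that cohort has one dose and no concurrent control, so a change within the session cannot be attributed to taVNS

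*Combined protocol and SAP*

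**What the plan says.** Section 1.0 titles Aim 3 as an assessment of tolerability and feasibility. Its hypothesis then goes further: taVNS "will be well tolerated and will modulate autonomic arousal and fear processes", as shown by physiological indicators.

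Section 3.0, separately from the aim, gives the purpose of this cohort: "This dose will be administered to individuals with anxiety and trauma symptoms to ensure that effects are sustained and to determine feasibility and tolerability". Section 6.0 gives the size: "Then this dose will be administered to 40 individuals with anxiety and trauma related symptoms". Neither section names a comparator.

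Other text does not fit a single-dose cohort of 40:

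- Section 1.0 says the dosing findings "may be evaluated an additional sample of 45 participants seeking treatment for anxiety or trauma related disorder".
- Section 10.0 states: "Participants in the taVNS group (not having implanted VNS) will be randomized to one of 9 doses with 5 participants per dose". It does not restrict this to healthy participants.
- Section 12.0 says the second sample of 45 is there in case of data loss and "to replicate dose-response findings/assess feasibility/tolerability on participants with anxiety or trauma related disorder or symptoms".
- Section 5.0 mentions balancing the sexes across active durations and sham conditions, although no sham-only group is defined anywhere.

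Within the session, Section 3.0 specifies: "All active sessions per dose will be delivered contiguously and at the end of the stimulation period, and sham stimulation at the beginning". The last recording in Section 10.0 is a recovery period of 5 to 10 minutes. The only analysis named in Section 12.0 is MCP-Mod on pre-to-post change. No Aim 3 test, decision rule or tolerability criterion is given.

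**The concern.** That taVNS modulates arousal is a causal statement. Without a concurrent control, the evidence for it would be a change over a long seated session with electrodes attached, a 90-minute stimulation period and a repeated oddball task run alongside a calming silent film. Heart rate, HRV, skin conductance and pupil size can all move over such a session with no stimulation.

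The plan itself treats elapsed time as something to hold constant: it fixes the total session length so that the pre-to-post interval is the same for everyone. That protects comparisons between durations in the healthy cohort. It gives no protection where everyone receives the same duration.

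Section 16.0 says the data will inform larger studies of taVNS paired with exposure therapy. A modulation finding produced by settling would carry forward into those studies.

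**Working it through.** **1. What can be reproduced.** Nine durations × 5 participants = 45, and 45 + 40 + 5 = 90, which agrees with Section 6.0. If the clinical cohort is 45, as in Sections 1.0 and 12.0, then 45 + 45 = 90 already and no room is left for the implanted-VNS group. The plan gives no alpha, power, effect size or SD for Aim 3, so 40 cannot be derived from a sample-size formula.

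**2. Which contrasts exist if there is one dose.**

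- *MCP-Mod.* It needs several doses and cannot be fitted to one.
- *Before versus after.* Available, but it combines stimulation with elapsed time.
- *Sham lead-in versus active, within the session.* Lead-in length = 90 − active duration, so 80 minutes at the 10-minute dose, 30 at 60 and 0 at 90. The order is always sham first, so stimulation site is confounded with time, and at 90 minutes there is no sham at all. Continuous heart rate and skin conductance recording, and the oddball task at 30, 60 and 90 minutes, describe the time course but do not remove this confounding.
- *Healthy low-dose participants.* They give some information on drift, but they are a different population and not randomised against the clinical cohort.

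**3. How often drift alone would look like an effect.** These inputs are assumptions, not figures from the plan: a paired t-test, two-sided 5%, no taVNS effect, and a non-specific drift δ in SDs of the change score.

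Formula: P = Pr(|T| > t₀.₉₇₅,ₙ₋₁), where T is noncentral t with n − 1 degrees of freedom and noncentrality δ√n. For n = 40 the critical value is 2.023; for n = 45 it is 2.015.

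| δ | δ√40 | P, n = 40 | δ√45 | P, n = 45 |
|---|---|---|---|---|
| 0 | 0 | 5% | 0 | 5% |
| 0.2 | 1.265 | 23% | 1.342 | 26% |
| 0.3 | 1.897 | 46% | 2.012 | 50% |
| 0.4 | 2.530 | 69% | 2.683 | 75% |
| 0.5 | 3.162 | 87% | 3.354 | 91% |

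A concurrent sham group with the same drift would hold this at 5%.

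**4. Whether the same 40 could carry a controlled test.** At an assumed two-sided 5% and 80% power, a 20/20 split detects (1.960 + 0.842) × √(1/20 + 1/20) = 0.89 SD. Only a large effect would be found, which is why the remedy below is a narrower claim and not a new arm.

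**5. Persistence.** The last described recording is the 5 to 10 minute recovery period. Return visits are described only for implanted-VNS participants. Nothing beyond that window can be shown.

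**6. Fear processes.** Section 4.0 lists fear learning and extinction among the contexts for ERPs without saying in which cohort. The procedures in Section 10.0 introduce the fear task under the implanted-VNS participants, and its risk paragraph on tasks refers to the same group. As written, the Aim 3 cohort may not do the task.

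**The case against.** The strongest reply is that Aim 3 is about tolerability and feasibility, which need no control, in what Section 16.0 calls a pilot. No alpha or go/no-go rule depends on modulation. This stands, and the tolerability part of the aim is not criticised here. It does not remove the causal hypothesis, which is in the aim's own text.

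Four stronger readings might be inferred, and the documents do not support them:

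- *That Aim 3 itself hypothesises sustained effects.* It does not. The phrase "to ensure that effects are sustained and to determine feasibility and tolerability" is in Section 3.0, and it may mean that effects seen in healthy participants carry over to patients. On that meaning the length of the recovery recording is beside the point.
- *That the cohort is definitely single-arm and single-session.* One dose is the likeliest reading of Sections 3.0 and 6.0, but Sections 5.0, 10.0 and 12.0 conflict with it. If the cohort were randomised across durations, a dose comparison would exist and deleting the modulation hypothesis would be the wrong remedy. A single session is stated only in connection with the healthy cohort and is inferred for this one.
- *That before versus after is the only contrast.* The sham lead-in, the repeated recordings and the healthy low-dose participants exist. They are weak for attribution, for the reasons in the working, but they are not absent.
- *That 23% to 87% is the trial's false-positive rate.* The plan names no Aim 3 test, and both the test and the drift are assumed.

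**Conclusion.** The point holds in limited form. If the anxiety/trauma cohort receives one selected duration, the described design cannot support the statement that taVNS modulates autonomic arousal or fear processes, because no available contrast separates stimulation from time in the session. That conclusion does not depend on the size of any drift.

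The size is illustrative. With no taVNS effect, assumed drifts of 0.2, 0.3, 0.4 and 0.5 SD of the change score give a significant paired test in about 23%, 46%, 69% and 87% of trials at n = 40, and slightly more at n = 45.

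Two narrower points also stand. Persistence beyond the 5 to 10 minute recovery recording cannot be shown, if that is what Section 3.0 means. And the fear part of the hypothesis may have no measurement in this cohort. Tolerability and feasibility are unaffected.

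**What to change.** 1. Reconcile the description of the clinical cohort. Sections 3.0 and 6.0 (one dose, 40 participants) must be made to agree with Section 1.0 (45, and optional), Section 5.0 (sham conditions), Section 10.0 (randomisation to nine durations) and Section 12.0 (45, replication of dose-response). This comes first, because the remaining changes depend on it.
2. If the cohort is single-dose, limit the Aim 3 hypothesis and conclusions to tolerability and feasibility. Report pre-to-post physiology as exploratory and descriptive, with confidence intervals, and state that it is not evidence of a taVNS effect.
3. In Section 3.0, delete the reference to sustained effects, or limit it to the recovery window, or reword it if carry-over from healthy participants is meant.
4. Remove fear processes from the Aim 3 hypothesis unless the fear task is given to this cohort, in which case Section 10.0 should say so.

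The cost is wording and a more modest Aim 3 claim. No sham arm, extra visit or extra participant is needed.

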## 2.0 Background

The vagus nerve is the longest cranial nerve and maintains parasympathetic control over the heart, lungs, and digestive track, while also providing the prefrontal cortex with somatic and visceral feedback (Chalmers et al., 2014; Porges, 2001). It contains a variety of fibers which provide sympathetic and parasympathetic innervation and carry somatic and visceral afferent and efferent information. Given the vagus nerve's contributions to cardiac functioning, it is often indexed using heart rate variability (HRV; beat-to-beat changes in the heart rate), also referred to as vagal tone. Pharmacological blockade of the vagus results in increased heart rate suggesting that cardiac activity is regulated by inhibitory vagal control. Chronic stress, on the other hand, leads to protracted sympathetic disinhibition, inflexible parasympathetic activity, and maladaptive cognitive responses. In fact, low vagal tone and poor inhibition of sympathetic activity (i.e., fight-or-flight) is implicated in a range of psychiatric conditions and mental health problems, including emotion regulation difficulties, anxiety, depression, and PTSD.

Aberrations in cardiac activity are central to both the state expression of anxiety, as well as its pathological form. During the acquisition of fear, the vagus nerve provides visceral feedback to the brain

and during extinction, the vagus inhibits sympathetic responses such as heart rate (Pappens et al., 2014). This critical brain-body communication which facilitates inhibitory fear extinction is hijacked in anxiety, as prolonged disinhibition of cardiac activity leads to persistent elevations in sympathetic responding regardless of the absence of threat. Thus, low vagal tone is considered a biomarker of anxiety and related psychopathology (Chalmers et al., 2014). Given that engagement in new learning (both reinforcement from positive feedback and inhibition of fear responses) are essential components to attain improvements via CBT and exposure

[figure not shown]

Figure 1. Moderating effect of RSA on the relation between negative cognitions and ERP indicator of cognitive control (Taylor et al., 2020).

therapy (Craske et al., 2008; 2014), it is predictable that disorders characterized by low vagal tone show poor treatment responsivity. In fact, our research suggests that parasympathetic responses are protective against the otherwise harmful effects of repetitive negative thinking (RNT) on cognitive control (Taylor et al., 2020; see Figure 1). Thus, given the linkage between vagal tone and psychiatric problems, interventions that non-invasively target the vagus nerve to regulate inhibition of sympathetic activity may be therapeutic for psychiatric conditions characterized by inflexible parasympathetic responses such as anxiety disorders.

Brain stimulation techniques have been used to identify mechanisms of action and treat mental health conditions, and evidence of afferent and efferent vagal contributions has been shown using a variety of stimulation techniques. In fact, vagal innervation of cardiac responses, observed via HRV, may be modulated using vagus nerve stimulation resulting in increases in parasympathetic activity (Zamotrincky et al., 2001), providing additional support for this connection. Stimulating the vagus also is a therapeutic intervention approved for the treatment of depression and can be accomplished by implantation of electrodes. Studies investigating VNS show that it affects brain regions linked to mood regulation, and clinical trials using VNS for depression show efficacy in reducing depressive symptoms, as well as reduced anxiety symptoms. A potential mechanism for its anxiolytic effects is that VNS stimulates the locus ceruleus, a primary norepinephrine (NE) site, which is essential to regulating arousal and stress responses. Those with anxiety and other related problems tend to show greater NE reactivity, thus VNS may aid its down regulation (George et al., 2000).

A draw back to administration of VNS is that it requires implantation, which reduces the feasibility of VNS as a tool for clinicians. Researchers have developed a safe, non-invasive, as well as easy to use stimulation technique, taVNS, which modulates afferent projections via stimulation of the vagus nerve through the human ear (Badran et al., 2018a; see Figure 2). Using conductive gel, an electrode is applied to the tragus cartilage of the left ear and pulsed electrical stimulation is delivered at a tolerable intensity for half hour to an hour, thus, stimulating the auricular branch of the vagus nerve (ABVN). This method has been shown to activate afferent vagal networks and early work shows promise for treatment of psychiatric conditions linked to overactive sympathetic responses (Badran et al., 2018c). Studies have recently demonstrated some efficacy for taVNS for reduction in symptoms of depression, including RNT, sleep disturbances and anxiety. However, mechanisms, parameters, and the neurobiological effects are not well established (Badran et al. 2018b). Trials studying the efficacy of taVNS have shown inconsistent results, which are largely attributable to incomplete consideration of stimulation parameters and corresponding modulation in the psychophysiological profile taVNS purportedly targets. This study aims to parameterize, then employ this emerging form of stimulation and explore its effects on learning and cognitive control, while fully evaluating the physiological mechanisms which are affected during and after stimulation.

Figure 2. TaVNS active and sham stimulation electrode placement

